ID: IB2019-METAGIST

Patterns of Care and Outcomes of Patients With METAstatic Gastrointestinal Stromal Tumors (METAGIST)

NCT03963544

Sept 1, 2018

Title	
METAGIST
 
Patterns of care and outcomes of patients with METAstatic GIST in a real-life setting: the METAGIST national observational study from the GSF-GETO

Rational	
Gastro intestinal stromal tumors (GIST) are rare mesenchymal tumors of the gastrointestinal tract characterized by somatic mutations in the gene encoding the KIT or the PDGFR alpha protein. Treatment of localized forms relies on adequate surgery without tumor spillage and systemic treatment with imatinib according to risk of relapse defined by localization, tumor size and mitotic count, as well as mutational status. Advanced and relapsing forms are currently treated with oral tyrosine-kinase inhibitors (TKI) of KIT and PDGFR such as Imatinib, Sunitinib and Regorafenib. Over two decades significant changes in drug discovery have impacted treatment strategies, notably via patient's access to various clinical trials. The use of focal treatments such as surgery or interventional radiology with mini invasive procedure of oligometastasis is also being proposed in some cases.
 
There is no precise data on patterns of sequential treatments used, especially proportions of patients with metastatic GIST eventually benefiting from access to a clinical trial or a focal treatment strategy in the course of their disease, and their results in terms of survival on a real life national level.
 
Using the French sarcoma Group national database we aim at describing treatments strategies proposed patients with metastatic GIST in the real life setting.

Objectives	
Primary objective
 
To describe clinic-biological profiles, patterns of care and modalities of treatment of patients with metastatic GIST in a real-life national setting.
 
Secondary objectives
 

- time to next treatment (TNT)

- overall survival

- proportion of patients included in a clinical trial during the course of their disease

-

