Material and Methods	
Inclusion
 
 
- patients <math>\geq</math> 18 years old
 
- with a diagnosis of metastatic GIST (metastatic at diagnostic or metastatic relapse)
 
- From 1990 to 2018
 
- with histological review performed by members of the pathological sub-committee of the GSF-GETO
 
- treated in one of the participating national reference network centers members of the GSF-GETO
 
- included in the prospectively maintained database of the GSF-GETO: the ConticaGIST
 
 
Methods
 
Descriptive data (see SARCOMABCB DICTIONNARY)
 
 
- Initial patients characteristics: age, gender, PS
 
- tumor characteristics : date, histology, location, size, mitotic count, miettinien classification, mutational status
 
- Initial treatment : initial surgery type, date, margins, tumor spillage, adjuvant systemic treatment (start and stop date)
 
- Metastatic disease characteristics : date, PS, location of metastasis
 
- Treatment in the metastatic setting : molecule used (start and stop date, best RECIST response), locoregional treatment performed, inclusion in a clinical trial
 
- Latest status : date, patient lastest Status, tumor latest status
 
 
Survival data
 
 
- Time to next treatment (TNT) TNT defined as the time from the systemic treatment onset to the next treatment or death due to any cause, whichever came first. When neither death nor new systemic therapy is observed, TNT is censored at the date of last patient contact.
 
- Overall survival in the metastatic setting (OS) defined as the interval between the diagnosis of metastatic disease or the first-line systemic therapy onset and the time of death. When death is not observed, OS is censored at the date of last patient contact.
 

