Statistics	
Statistical analysis of the baseline demographics and clinical outcomes will be based on all data available up to the cut-off date of December 31, 2018. Descriptive statistics will be used to show the distribution of variables in the population. Multivariate logistic regression models will be used to identify biological and clinical factors associated with the type of treatment received and with the probability of survival 5 years after the diagnosis of metastases. Follow-up times will be described as median values based on the inverse Kaplan–Meier estimator. Prognostic factors of TNT and OS will be identified using Cox proportional hazard models. The variables included in the univariate and multivariate analyses are the descriptive data.

	The correlation between TNT and OS will be evaluated at each of the four first-lines of metastatic chemotherapy by a Spearman rank correlation coefficient and expressed as a value between 0 (no association) and 1 (perfect association). We will use a reviewed copula-based approach that introduces an iterative multiple imputation method for the estimation of the correlation coefficient. The data will be analyzed using the SAS v9.3 and R v3.3 software packages.
Timeline	February 2019 : end of collection of data and updating of the conticaGIST March - April 2019 : first version statistical analyses
Ref	
 
 
 
 

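### The logistic models for type of treatment received set no time window, at-risk set or handling of death, so for trial inclusion or focal treatment they would mix access with time alive and time observed

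*Combined protocol and SAP*

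**What the plan says.** The Statistics section plans that "Multivariate logistic regression models will be used to identify biological and clinical factors associated with the type of treatment received". The same sentence also applies logistic regression to survival, and there it fixes a horizon of 5 years from the diagnosis of metastases. The treatment outcome has no horizon, and its categories are not listed.

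Two other places show what kind of treatment outcome is of interest. A secondary objective is the "proportion of patients included in a clinical trial during the course of their disease". The Rational section notes the lack of data on patients "eventually benefiting from access to a clinical trial or a focal treatment strategy in the course of their disease".

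Observation time is very unequal. Patients are included "From 1990 to 2018" (Material and Methods, Inclusion), and the analysis uses "all data available up to the cut-off date of December 31, 2018" (Statistics).

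On covariates, "The variables included in the univariate and multivariate analyses are the descriptive data". The descriptive data include the date of metastatic disease. On follow-up, "Follow-up times will be described as median values based on the inverse Kaplan–Meier estimator", with no link to the logistic models. Cox models are planned only for time to next treatment (TNT) and overall survival (OS).

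The metastatic treatment variables are "molecule used (start and stop date, best RECIST response), locoregional treatment performed, inclusion in a clinical trial". In that list only the drugs carry dates.

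**The concern.** Trial inclusion and focal treatment can happen at any point after metastasis, but only while the patient is alive, and they are recorded only while the patient is observed. A received/not received outcome scores as equally untreated a patient who died at six months, one diagnosed in 2018 and one followed for 15 years. The model has no time axis with which to tell them apart.

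The resulting odds ratios would be read as showing which patients get access. In part they would restate which patients live longer and which were diagnosed earlier. Patterns of care is the primary objective, and this is the only planned regression that explains treatment received.

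Nothing else in the plan fills the gap. TNT counts death as an event alongside the next treatment, so its Cox model does not isolate access either.

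**Working it through.** The plan states no access rate, survival figure or sample size, so there is no figure of its own to reproduce. All hazards below are assumptions.

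**Inputs from the documents.** Entry from 1990 to 2018 and a cut-off of 31 December 2018 give potential follow-up from about 0 to about 29 years.

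**Model.** Let a be the access hazard, d the death hazard and C the potential follow-up, with hazards constant:

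P(ever treated by C) = a/(a+d) × (1 − exp(−(a+d)C)).

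With complete follow-up this is a/(a+d). The odds are then a/d, and a factor that changes only d has an odds ratio (OR) of 1/HR, where HR is its death hazard ratio.

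**1. Survival effect, no true effect on access.** Take a = 0.10 per year and median OS 5 years, so d = ln 2/5 = 0.1386. With a death HR of 2, d = 0.2773.
- Complete follow-up: 0.10/0.2386 = 41.9% against 0.10/0.3773 = 26.5%, OR 0.50.
- Follow-up uniform over 0 to M = 19 years: averaging over C gives P = a/(a+d) × [1 − (1 − exp(−(a+d)M))/((a+d)M)], which is 32.8% against 22.8%, OR 0.61. A simulation of the same set-up (40 runs of 200,000 patients) also gave 0.61. In it the cause-specific hazard ratio for access, censoring at death and end of follow-up, was 1.00, the true value.

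**2. Range.** Death HR 2, no effect on access, median OS 3 to 7 years, access 0.05 to 0.20 per year:

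| Potential follow-up | Spurious OR |
|---|---|
| 2 years | 0.78–0.90 |
| 5 years | 0.59–0.78 |
| 10 years | 0.51–0.65 |
| 20 years | 0.50–0.54 |

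**3. Follow-up alone.** With identical hazards (a = 0.10, median OS 5 years), 15.9% are ever treated with 2 years of potential follow-up, 29.2% with 5 and 38.1% with 10. Comparing 2 with 10 years gives OR 0.31. Over the range of hazards in step 2 it is 0.25 to 0.43.

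**4. When the direction changes.**
- A factor that doubles the death hazard and also raises the access hazard 1.5-fold (base 0.10 per year, median OS 5 years) gives OR 1.34 at 2 years, 1.09 at 5 and 0.86 at 10. The same true effect changes sign with follow-up.
- A later line follows progression. Suppose a factor doubles only the progression hazard, from 0.2 to 0.4 per year, with death before progression 0.03 per year, death after progression 0.3 per year, and every patient who progresses starting second line. Median OS falls from 6.0 to 4.5 years. Putting the progression hazard for a and 0.03 for d, the OR for ever starting second line is 2.45 at 2 years (32.1% v 53.7%), 3.15 at 5, 3.10 at 10 and 2.15 at 20.

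**The case against.** **The outcome is undefined, not stated to be ever/never.** A reader might infer that the plan commits to ever/never models for trial entry, focal treatment and later lines. It does not. The Statistics section refers only to the type of treatment received, and the cumulative wording comes from the Rational section and a secondary objective, both of which concern proportions. If the sponsor means only the choice of first-line treatment, the problem largely disappears. This stands. Ever/never remains the natural reading for trial and focal treatment, and the plan gives no other.

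**The plan claims association, not cause.** The primary objective is descriptive and descriptive statistics are planned separately, so a biased regression does not make the whole patterns-of-care answer wrong. This also stands. With complete follow-up, an ever/never odds ratio would even be a fair description of who is eventually treated, although not of access among those alive. With follow-up from about 0 to 29 years it is neither.

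**Date of metastatic disease is a covariate.** It could absorb part of the difference in administrative follow-up. But it would mix follow-up with changes in practice over the period, and it cannot deal with death as a competing event.

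**The sizes rest on assumed hazards.** Correct. An odds ratio of exactly 0.50 is the limiting case of constant hazards, a death HR of 2, no effect on access and complete follow-up.

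**Conclusion.** The point holds where the outcome can occur at any time in the disease course, as trial inclusion and focal treatment can. There, logistic regression without a window, at-risk set or handling of death mixes access with survival and follow-up. A factor that shortens life without changing the access rate will appear to reduce access, and recently diagnosed patients will appear to have less of it.

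For an assumed death HR of 2 the spurious OR is modest at 2 years (0.78–0.90), substantial at 10 years (0.51–0.65) and about 0.61 in the mixed follow-up example. These figures assume constant hazards, median OS of 3 to 7 years and access of 0.05 to 0.20 per year; the mixed example uses 5 years and 0.10 per year.

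A reader might go further and infer that any factor that shortens life will seem to reduce access, later lines included. That does not follow. If the factor also raises the access rate, or acts through progression to a next line, the odds ratio can exceed 1. The change is one that should be made before analysis. It does not call the study's descriptive results into question.

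**What to change.** Define each treatment outcome and who is at risk for it.

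1. **Choices at a common time point.** Keep logistic or multinomial regression: first-line type among those who start first line, and line-k type among those who start line k. This also gives later lines a proper risk set.
2. **Trial inclusion and focal treatment.** Analyse time from metastatic diagnosis to first receipt with cause-specific Cox models. Treat death as the competing event and censor at last patient contact, no later than the cut-off, in line with the plan's censoring of OS and TNT. Report absolute proportions by Aalen-Johansen cumulative incidence.
3. **Where no date is held.** The Methods list dates the drugs but not locoregional treatment or trial inclusion; the data dictionary it cites was not available for this review. A trial-entry date may be taken from the start of the corresponding line. Otherwise, model receipt by line among those who start that line, or state that the odds ratios are not adjusted for survival and follow-up.

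If only first-line choice was intended, one sentence saying so is enough for these models.

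The cost is revised wording, standard analyses in the software already named, two effect measures to report (odds ratios and hazard ratios), and a check of date availability. If the dates are largely absent, item 2 may be possible only for some outcomes.

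### The logistic model for survival 5 years after metastases has no follow-up requirement, so metastases diagnosed after 31 December 2013 can enter only as deaths or as unknown status

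*Combined protocol and SAP*

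**What the plan says.** The Statistics section sets multivariate logistic regression to look for patient and disease features "associated with the type of treatment received and with the probability of survival 5 years after the diagnosis of metastases". The data are "all data available up to the cut-off date of December 31, 2018", and the Timeline gives "February 2019 : end of collection of data and updating of the conticaGIST", so no later follow-up is planned.

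Under Inclusion the period is "From 1990 to 2018". It is not said whether this dates the GIST or the metastases, but on either reading metastases diagnosed in 2014 to 2018 are eligible. No criterion asks for a minimum follow-up.

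The candidate variables are the descriptive data. They include "Metastatic disease characteristics : date, PS, location of metastasis", prior "adjuvant systemic treatment (start and stop date") and "Treatment in the metastatic setting : molecule used".

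Censoring is defined under Survival data for the time-to-event endpoints only. For OS: "When death is not observed, OS is censored at the date of last patient contact". The multiple imputation in the Statistics section serves only the TNT-OS correlation. Nothing restricts, weights or imputes patients in the 5-year logistic model.

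**The concern.** A standard logistic model needs a known yes or no for each patient and cannot use a censored time. For metastases diagnosed in the last 5 years before cut-off, yes is unobservable by construction. Patients diagnosed earlier but lost before 5 years are also of unknown status.

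The analyst must therefore choose a handling that the plan does not name. If unknowns are dropped, recent diagnoses contribute deaths and no survivors. If they are coded alive, recent diagnoses contribute too many survivors. The two errors run in opposite directions, so no net direction can be claimed from the text.

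The model's purpose is to identify prognostic factors. A factor fixed at metastatic diagnosis that has no effect on survival, but became more or less common over the inclusion period, can appear associated with 5-year survival. Prior adjuvant treatment is a possible example, if its use changed over the window (an assumption). The Rational section itself says that treatment strategies changed over two decades.

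Treatments received after metastatic diagnosis, and trial inclusion, have a separate problem: patients must live long enough to receive them. No direction is claimed for those variables here.

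**Working it through.** **1. The date boundary (documents only).** Metastases diagnosed on 31 December 2013 reach 5 years on 31 December 2018, the cut-off. Those diagnosed on 1 January 2014 reach it on 1 January 2019, after the cut-off. The period 1 January 2014 to 31 December 2018 is 1,826 of the 10,592 days from 1 January 1990, or 17.2%. Using information up to the end of data collection would move the boundary by at most about 2 months.

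**2. Assumptions for size.** The plan has no figure to reproduce: it states no cohort size, accrual, loss or survival. Assumed:
- metastatic diagnoses uniform over W = 29 years (1990-2018) or 19 years (2000-2018);
- exponential OS with median 3, 5 or 7 years, hazard l = ln 2 / median;
- loss to follow-up c = 0 or 0.05 per year.

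This makes 12 scenarios. For potential follow-up u and h = min(u, 5):
- death seen = l/(l+c) × (1 − exp(−(l+c)h));
- survivor seen = exp(−5(l+c)) if u ≥ 5, otherwise 0;
- the rest are unknown.

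**3. One case by hand (median 5, W = 29, no loss; true 5-year survival 50%).**
- Diagnosed after 2013: 5/29 = 17.2% of patients.
- Of these, seen to die: 1 − (1 − 0.5)/0.693 = 27.9%. Survivors: 0%. Unknown: 72.1%.
- Whole cohort: survivors 0.828 × 0.5 = 0.414; deaths 0.414 + 0.172 × 0.279 = 0.462; unknown 0.172 × 0.721 = 0.124.
- Dropped: 0.414/(0.414 + 0.462) = 47.3%. Coded alive: 0.414 + 0.124 = 53.8%.

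**4. Across scenarios.** With W = 19, 5/19 = 26.3% of patients are diagnosed after 2013. Unknown status affects 10.2% to 20.8% of all patients without loss and 21.8% to 34.1% with loss. At median 5 (true 50.0%), fitted 5-year survival is:

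| | W = 29, no loss | W = 19, no loss | W = 29, 5%/year | W = 19, 5%/year |
|---|---|---|---|---|
| Dropped | 47.3% | 45.5% | 43.6% | 41.8% |
| Coded alive | 53.8% | 55.8% | 58.4% | 60.1% |

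**5. Odds ratio for survival of a factor with no effect (true value 1).** These are expected-value logistic fits on a fine grid of u, with ranges over the 12 scenarios. The factor's prevalence follows one of three assumed patterns.

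| Prevalence over calendar time | Linear date: dropped | Linear date: coded alive | No date: dropped | No date: coded alive |
|---|---|---|---|---|
| Linear rise, 20% to 80%, over the window | 1.00 | 1.00 | 0.82-0.89 | 1.14-1.37 |
| Step, 10% to 60%, ten years before cut-off | 0.93-1.08 | 0.88-1.03 | 0.76-0.79 | 1.22-1.40 |
| Gradual rise, 10% to 60%, over the last 10 years | 0.83-0.86 | 1.11-1.26 | 0.69-0.77 | 1.32-1.65 |

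The no-date columns matter only if the univariate analyses cover this model.

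Other forms of date:
- Quadratic date gives 0.94-1.00 (dropped) and 0.98-1.04 (coded alive) for the gradual pattern, but 1.10-1.18 and 0.87-0.93 for the step.
- Five-year periods (no loss) with unknowns dropped give 1.00, but the 2014-2018 coefficient cannot be estimated because that period has no survivors. Coded alive, they give 1.00 (step) and 1.05-1.11 (gradual).

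**6. Factor unrelated to calendar time (hazard ratio 1.5).** Dropping shifts the odds ratio by at most 2.3%. Coding alive lowers it by 3% to 19%. For example, at reference-group median 5, W = 29 and no loss, the odds ratio for death is 1.83 in truth, 1.84 dropped and 1.75 coded alive.

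**7. After restriction to diagnoses through 2013.** The null odds ratio is 1.00 for all three patterns. With 5%/year loss and no weights, fitted survival is 28.3%, 46.5% and 57.6% (medians 3, 5, 7) against true 31.5%, 50.0% and 61.0%. Inverse-probability-of-censoring weights recover the true values. A simulated Cox model for OS with the gradual null factor (median 5) gives hazard ratios of 0.992 to 1.000.

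**The case against.** The strongest case is that little depends on this model. The primary objective is descriptive, 5-year survival is not among the secondary objectives, and prognostic factors for OS already have a Cox model that handles censoring. This stands and limits the severity.

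Date of metastatic disease is a listed covariate, and only one assumed pattern gives a bias of consistent direction once date enters linearly. This also stands. But the plan does not say in what form date enters, no form tried removes the problem in every case, and adjusting for date does not define the outcome of a patient last seen alive at 2 years.

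The model is meant to find factors, not to estimate 5-year survival, so the survival percentages show the mechanism and the odds ratios carry the weight. Without a cohort size, nobody can say whether these shifts exceed sampling error.

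It can be said that the plan omits a rule and does not prescribe a wrong one. True, but the stated data scope points away from restriction, and both default handlings can bias the result.

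Finally, restriction gives exactly 1.00 only if survival is stable over calendar time. If median OS rose linearly from 3 to 7 years over the window (assumed, no loss), the restricted odds ratio would be 1.10 to 1.30 without date and 0.97 to 1.00 with linear date. That is ordinary confounding by period. It is a reason to keep date in the restricted model and does not undo the restriction.

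**Conclusion.** The concern holds. The 31 December 2013 boundary follows from the plan's own dates, and no rule for unknown 5-year status exists for this model. The size is illustrative and rests on assumed accrual, survival, loss and prevalence trends. With date entered linearly, the distortion of a null odds ratio ranges from none to about 17% when unknowns are dropped (0.83) and about 26% when they are coded alive (1.26). A factor unrelated to calendar time is little affected by dropping. The fault is confined to one secondary analysis; the Cox model for OS and the descriptive analyses do not share it. It should be fixed before the analysis is run, because the result depends on an unstated choice.

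**What to change.** Add to the Statistics section: *The 5-year survival model includes patients with metastases diagnosed on or before 31 December 2013; patients lost before 5 years are handled by inverse-probability-of-censoring weights.* State the variables in the weight model, and keep date of metastatic diagnosis as a covariate with its form specified.

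Alternatively, drop this model and report Kaplan-Meier 5-year survival alongside the Cox model already planned.

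The cost is a short addition to the text and standard SAS or R code, with no new data. Under restriction, the 2014-2018 diagnoses (17% to 26% of patients under the assumed accrual) leave this one analysis, which then says nothing about them; they stay in the Cox and descriptive analyses. The weights assume that loss is unrelated to survival given the variables in the weight model. Neither the restriction nor the weights remove the dependence of post-metastatic treatment variables on surviving long enough to be treated.

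### The covariate rule for the OS Cox model admits treatments, trial inclusion and best response that can arise after time zero, and sets no timing rule, so an ordinary fixed fit carries immortal-time bias

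*Combined protocol and SAP*

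**What the plan says.** The Statistics section plans Cox models for both time-to-event outcomes: "Prognostic factors of TNT and OS will be identified using Cox proportional hazard models". It also plans logistic models: "Multivariate logistic regression models will be used to identify biological and clinical factors associated with the type of treatment received". A second logistic outcome is being alive five years on from metastatic diagnosis. One sentence then fixes the covariates: "The variables included in the univariate and multivariate analyses are the descriptive data".

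Descriptive data is a heading in Material and Methods. It covers characteristics at initial diagnosis and at metastatic diagnosis, and under treatment in the metastatic setting it lists "molecule used (start and stop date, best RECIST response), locoregional treatment performed, inclusion in a clinical trial". Its last item is the latest status of patient and tumour.

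The Survival data section defines OS as "the interval between the diagnosis of metastatic disease or the first-line systemic therapy onset and the time of death", which leaves two possible starting points. The Objectives count trial inclusion over the whole disease course, and the Statistics section refers to four metastatic lines. Nowhere does the plan limit covariates to those known at time zero, call for time-dependent covariates or set a landmark.

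**The concern.** Second and later lines, and best response on treatment, necessarily come after either OS starting point. Focal treatment and trial entry can. A patient who dies early cannot acquire them. If such a variable enters a Cox model as fixed ever/never, the survival time before the event is credited to the exposed group. A factor with no effect on the hazard then looks protective.

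The two OS time zeros add to this. First-line treatment is known at time zero if OS starts at first-line onset, but not if it starts at diagnosis of metastases.

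OS is a secondary objective, and the rationale says that data are lacking on "access to a clinical trial or a focal treatment strategy in the course of their disease, and their results in terms of survival". The exposed variables are thus the ones that motivate the study. Factors that only mark longer survival could be reported as favourable prognostic factors.

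**Working it through.** The plan states no sample size, event count or effect size, so there is no figure of its own to reproduce. The check asks what a fixed fit returns when the true effect is nil.

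**Inputs.** Only the calendar window comes from the documents: "From 1990 to 2018" in the Inclusion list, 29 calendar years. Everything else is assumed: median OS 5 years, 30% lifetime access to a trial, a share p0 of that access already present at time zero (0, 25, 50 or 75%), diagnoses spread evenly over the window, and a shorter 19-year window as an alternative.

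**Model.**
- Death: T exponential with rate ln 2 / 5 = 0.1386 per year. Censoring: C uniform on (0, 29) or (0, 19).
- Later entry: E exponential and independent of T, so the true HR is 1. Among patients without access at time zero, the required probability of entry before death is q = 0.30(1 − p0)/(1 − 0.30 p0). The entry rate is 0.1386 × q/(1 − q), which is 0.0594, 0.0446, 0.0297 and 0.0149 for the four shares.
- Ever exposed means E < min(T, C). Each case used 500,000 simulated patients.

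**Results for the OS Cox model (true HR 1).**

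| Access at time zero | 0% | 25% | 50% | 75% |
|---|---|---|---|---|
| Ever/never HR, 29 years | 0.41 | 0.50 | 0.63 | 0.79 |
| Ever/never HR, 19 years | 0.42 | 0.53 | 0.66 | 0.81 |
| Ever/never HR, range over 18 scenarios | 0.30–0.46 | 0.38–0.58 | 0.51–0.72 | 0.69–0.85 |

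The 18 scenarios cross median OS of 3, 5 and 7 years, access of 20, 30 and 50%, and the two windows. In the same 72 runs (18 × 4 shares) the time-dependent HR was 0.99–1.01 and the 2-year landmark HR 0.98–1.02.

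**Adjustment does not remove the bias.** With a baseline factor of HR 2 that also halves access (30% prevalence, 29 years), the adjusted ever/never HRs are 0.40, 0.51, 0.64 and 0.81. The adjusted time-dependent HRs are 1.01–1.03.

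**Other listed variables, also given no effect.**
- Ever reaching a third line (first line median 2 years, second 1 year): ever/never HR 0.17, time-dependent HR 0.97.
- Best response reached between 0.15 and 1.0 years: ever/never HR 0.82, and 1.00 from a 1-year landmark.

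The bias is smaller for early events and larger for late ones.

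**A second simulation with different inputs.** With 600 patients per replicate, 60 replicates per scenario, median OS 36, 60 or 84 months, median wait 24, 60 or 120 months and no access at time zero, the mean fixed HR was 0.20–0.44, with p < 0.05 in every replicate. The time-dependent HR was 0.96–1.02.

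**When entry marks worse prognosis.** If late entry doubles or triples the death hazard, with no access at time zero, the ever/never HR is still 0.64 or 0.79 over 29 years. The time-dependent HR is 2.00 or 2.99. The bias can therefore reverse the sign.

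**5-year logistic model, if the covariate sentence governs it.** Among patients with at least 5 years of potential follow-up, the spurious odds ratio for survival across the four shares is 2.5, 1.8, 1.4 and 1.2 when only entry before year 5 counts. When entry at any time counts, it is 5.6, 3.5, 2.2 and 1.5 over 29 years, and 5.0, 3.1, 2.1 and 1.4 over 19 years.

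**The case against.** The strongest reply is that the plan never says ever/never. A Cox model can take time-dependent covariates, and start and stop dates are collected for molecules. The covariate sentence may also be only a pointer to a variable list: read literally, it would put latest patient status, the OS outcome itself, into the OS model, which no analyst would do. This stands as a limit on the claim: the bias is conditional on coding that the plan leaves open. It does not remove the gap. Unlike latest status, treatments and trial inclusion are plausible covariates, so the pointer reading does not exclude them, and the list is still tied to no time zero.

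The stakes are secondary. The primary objective is descriptive, and no objective names a treatment comparison. That is correct.

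The direction of the reported result is not assured either. If entrants at time zero also carry a doubled hazard, with a 50% time-zero share, the ever/never HR is 1.06 (29 years) or 1.16 (19 years). The bias still runs toward benefit, but the reported factor need not look favourable. The statement about false favourable factors therefore applies to those that only mark longer survival.

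The logistic model may fall outside the rule, because its own sentence speaks of biological and clinical factors and treats type of treatment as an outcome. That part remains likely rather than certain.

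**Conclusion.** The concern holds and should be fixed. The covariate rule for the OS Cox model admits variables that can arise after time zero and gives no instruction on their timing, so an ordinary fixed fit that follows it carries immortal-time bias. In the assumed cases with no true effect, the ever/never HR for trial inclusion runs from 0.30 to 0.85, depending mainly on how much access is already present at time zero. Correct coding returns about 1. These sizes rest on exponential survival, an independent wait to entry and uniform accrual, and they are not estimates for this cohort.

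The effect is confined to the secondary prognostic models. The descriptive results and the proportion included in a trial are untouched. In TNT models for a given line, treatment at that line and earlier treatments are legitimate baseline covariates; best response at that line is not.

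**What to change.** Replace the covariate sentence in the Statistics section with:

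> Each model names its time zero, and its covariates are limited to descriptive variables known at that time. In the OS Cox model, treatments and trial inclusion that start after time zero enter as time-dependent covariates or from a prespecified landmark, and best response enters from a landmark. The 5-year logistic model uses only variables known at diagnosis of metastases, or is restated from a landmark. In line-specific TNT models, treatment and trial participation at that line and earlier treatments are baseline covariates, and best response at that line enters only from a landmark. Latest-status variables are never covariates.

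The cost is one paragraph and modest programming. Material and Methods shows dates for molecules but none for locoregional treatment or trial inclusion. The data dictionary it cites may hold them, so this must be confirmed in the database; factors without dates should be described only.

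There are three downsides. Hazard ratios will probably look less favourable. A 2-year landmark sets patients aside: in the assumed case 1 − 0.5^(2/5) × 27/29 = 0.29 over 29 years, or 1 − 0.5^(2/5) × 17/19 = 0.32 over 19 years. And the estimates remain prognostic associations, not treatment effects.
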